6. ASSESSMENT AND FOLLOW-UP

Direct participant involvement will finish after the results of the LFIA test are uploaded. Follow up thereafter will be via the respective registries for 6 months. The study will end at the time the last participant reaches 6 months from the point of their registration on the study web portal.

Participants will have access to an information booklet which describes the meaning of the test results. Participant's GPs will not be informed of recruitment.

7. STATISTICS AND DATA ANALYSIS

Data collection will be undertaken in collaboration with implementation partner Ipsos MORI. The data from the participants is self-entered into an online questionnaire hosted on a secure web portal developed and managed by Ipsos MORI.

Ipsos MORI will be responsible for setting up and managing the study web portal, receiving the questionnaire data, setting up and entering the questionnaire data into the study database and linking in the uploaded results of lateral flow assay. Once data is complete, a copy of the study database for each patient population will be sent securely from Ipsos MORI to NHSBT and NDRS where it will be linked to routinely collected healthcare data on COVID-19 infection, and severe outcome over the subsequent 6 months and analysed.

Analysis for the a) solid organ transplant groups and b) rare autoimmune disease and cancer groups will be conducted using a common protocol and statistical analysis plan, but separately by NHSBT and NDRS respectively, due to the complexities of data sharing between the two registries and existing restrictions on the data sharing they have with NIMS and NHS Digital. The high-level analysis plan is as follows:

1. The proportion of patients (and 95% CI) with and without antibodies to SARS-CoV-2 at least 21 days post 3rd vaccine and prior to 4th vaccine dose will be presented.
2. The proportion of patients (and 95% CI) with and without antibodies to SARS-CoV-2 following a 4th vaccine dose will be presented
3. The cumulative incidence (and 95% CI) of participants having at least one RT-qPCR proven infection in the 6-month follow-up will be presented for those with and without antibodies to SARS-CoV-2 at the time the study LFIA was undertaken. Risk-adjusted cumulative incidence rates will be compared using a Fine and Gray model. These methods allow for participants who may die during the follow-up period.
4. The cumulative incidence (and 95% CI) of participants hospitalised due to COVID-19 and deaths due to COVID-19 by 6 months will be presented for those with and without antibodies to SARS-CoV-2 at the time the study LFIA was undertaken and compared as described above if there are sufficient events.
5. Rates of those with and without antibodies to SARS-CoV-2 after 3rd or 4th vaccine (and 95% CI) will be presented for different clinical characteristics and

sociodemographic factors. Logistic regression models will be used to identify which of these factors are independently associated with developing antibodies following completion of the primary vaccine course.

6. The proportion of re-sampled transplant recipients (and 95% CI) with and without antibodies to SARS-CoV-2 following 4th dose who did not have antibodies after 3rd dose.

All outcomes will be adjusted for other known risk factors, and receipt of a subsequent 4th vaccine dose, as and where appropriate. Multiple imputation based on full conditional specification will be used to impute values of potential risk adjustment factors. The set of variables that will feature in the multiple imputation models will be described in the SAP. Sensitivity analyses will be conducted with cases with missing primary outcome data excluded.

A descriptive analysis aligned with above will additionally be performed for the young adult population.

Sample size

Each participant population will recruit 12,000 participants, and of these, we expect 85% to return their LFIA result (n=10,200). Following a third vaccine, we estimate approximately a third of participants in each group will have no SARS-CoV-2 antibodies, so this sample size will give a 95% confidence interval for the proportion of participants with no antibodies of $\pm 0.91\%$ for each participant group ^{7,8}. Even if the proportion of participants with no antibodies is 50%, the confidence interval would be $\pm 0.97\%$, so the large study size gives very good precision.

The study has been powered to detect a difference of 2% in the proportion of participants free from RT-qPCR proven infection in the 6-month follow-up period, with 90% power and a 5% two-sided significance level. We have assumed a 2:1 ratio between those with and without SARS-CoV-2 antibodies, as described above. In the group with SARS-CoV-2 antibodies it has been estimated that 92.4% will be free from infection at 6 months and to detect a decrease to 90.4% in the group without SARS-CoV-2 antibodies using survival analysis methods, we require 9,273 participants in total in each participant population (justification for the expected rate is provided in Appendix 1 (Reproducibility statistical and design annex)). Our planned recruitment of 10,200 LFIA results per group therefore allows for up to a 9% withdrawal rate, which we think is very achievable as patients will have opted-in to the study initially. Higher LFIA return rates, a lower withdrawal rate, or combining data across the patient populations would enable smaller differences to be detected. We think that the timing of the study, and early evidence of strong engagement, would mean that only a relatively small number of patients would have received their 4th dose at the time of recruitment. With the emergence of Omicron, we expect infection event rates observed in the study to now be higher than those used in the original sample size calculation, even if the 4th dose reduce rates of RT-qPCR positive infection.

DIAGNOSTIC ACCURACY OF THE IMMUNOASSAYS

Using the threshold value for positivity on serological testing of ≥ 7.10 BAU/ml (n=183) on Abbott Architect Assay and confirmatory DABA results for available discordant samples (n=3) as the reference standard, the overall performance of the test in these combined cohorts produce an estimate of sensitivity of 92.0% (115/125; 95% CI 85.8% to 96.1%) and specificity of 95.1% (58/61; 95% CI 86.3% to 99.0%).

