1.2. RATIONALE FOR CURRENT STUDY

Effective protection and management strategies of SARS-CoV-2 infection in immunocompromised adults have wide-reaching implications. For example, evidence has shown; a) they are more likely to have severe disease, which is associated with morbidity and mortality¹⁴⁻¹⁷; b) they are more likely to have prolonged infection, and viral shedding¹⁸; c) they are a risk for promoting viral evolution and escape mutations¹⁹.

Immunocompromised young persons (aged 12-17 years old) are also considered to be at heightened risk from SARS-CoV-2 infection. Recent studies have suggested that this group mounts stronger responses following SARS-CoV-2 vaccination than are observed in vaccinated immunosuppressed adults, but numbers of participants were small, and the Joint Committee on Vaccination and Immunisation (JCVI) has recommended that the immunocompromised young also should receive a booster vaccine following three primary vaccines⁴⁻⁶. Clarification of how this group respond to SARS-CoV-2 vaccination will inform future immunisation strategies.

The aim of this proposal is to assess at a population level; 1) the proportion of immunosuppressed people who have detectable SARS-CoV-2 antibodies following at least 3 vaccine doses, and the sociodemographic, disease, and treatment characteristics that influence antibody status; 2) if the detection of antibodies inversely correlates with subsequent risk of SARS-CoV2 infection and/or severity of disease in immunosuppressed individuals.

We aim to target patient groups least likely to mount an immune response to vaccination^{1,2,9}: a) solid organ transplant recipients; b) patients with a rare autoimmune disease; c) patients with haematological malignancies, specifically lymphoid malignancies. We will use comprehensive registries to identify and recruit patients

from these groups, and utilise the existing linkages these registries already have to obtain COVID-19 outcome information.

We hypothesise that a sizeable proportion of immunosuppressed people will have no detectable SARS-CoV-2 antibodies following either their third or fourth vaccine dose, and that this cohort is particularly susceptible to SARS-CoV-2 infection and death.

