2. STUDY OBJECTIVES

AIM:

The aim of this proposal is to evaluate the detection of SARS-CoV-2 antibodies at a population level in immunosuppressed individuals, by determining:

1. The proportion of immunosuppressed people who have detectable SARS-CoV-2 antibodies following a primary vaccine course (at least 3 doses), and the demographic, disease, and treatment characteristics that influence antibody status.
2. If the detection of antibodies inversely correlates with subsequent risk of SARS-CoV-2 infection and/or severity of disease in immunosuppressed individuals.

OBJECTIVES:

1. To estimate the proportion of immunosuppressed people with detectable SARS-CoV-2 antibodies by LFIA testing following a primary vaccine course (3 doses).
2. To estimate the proportion of immunosuppressed people with detectable SARS-CoV-2 antibodies by LFIA testing following a 4th vaccine dose.
3. To correlate antibody status with risk of subsequent RT-qPCR proven infection and disease severity in immunosuppressed people.
4. To describe clinical characteristics, e.g. immunosuppression burden and sociodemographic factors, associated with lack of detectable SARS-CoV-2 antibodies.

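### The Fine and Gray ratio planned in Section 7, items 3 and 4, suits absolute 6-month risk, but alone it cannot show whether antibody-negative people are infected at a higher rate while alive; a cause-specific hazard ratio should be prespecified beside it.

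*Combined protocol and SAP*

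**What the plan says.** Section 7, item 3, presents the cumulative incidence of RT-qPCR proven infection over 6 months, with 95% confidence intervals, by antibody status at the study LFIA. For the comparison, "Risk-adjusted cumulative incidence rates will be compared using a Fine and Gray model". The stated reason is that the methods accommodate deaths during follow-up. Item 4 applies the same comparison to COVID-19 hospitalisation and COVID-19 death if events are sufficient. Section 7 also plans adjustment for known risk factors and for a later 4th dose.

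No cause-specific hazard model is named anywhere, and neither is a comparison of competing deaths by antibody status.

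The questions the comparison serves are stated in two ways. Section 1.2 hypothesises, of people without antibodies, that "this cohort is particularly susceptible to SARS-CoV-2 infection and death". Objective 3 in Section 2 is "To correlate antibody status with risk of subsequent RT-qPCR proven infection and disease severity in immunosuppressed people". The sample size text in Section 7 says the study is "powered to detect a difference of 2% in the proportion of participants free from RT-qPCR proven infection" over 6 months, by survival methods, and does not mention competing death.

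**The concern.** A Fine and Gray model keeps people who have died of a competing cause in the risk set, where they can no longer have the event. Its subdistribution hazard ratio therefore combines two things: the rate of infection among people still alive and uninfected, and the rate at which each group loses people to other deaths. That is right for asking how many in each group will have had a proven infection by 6 months. It does not isolate whether lack of antibodies goes with a higher infection rate among the living, which is what a claim about susceptibility means.

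If antibody-negative patients died of other causes more often, the ratio would move toward 1 even with the infection rates among the living unchanged. Section 7 also has the transplant population and the autoimmune and cancer populations analysed separately by two registries. Each ratio would then absorb the mortality contrast of its own population, so different ratios might reflect different death patterns instead of different antibody associations. With only the one ratio reported, a reader could not tell.

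**Working it through.** **Inputs from Section 7.** Antibody-positive: "it has been estimated that 92.4% will be free from infection at 6 months". Antibody-negative: "to detect a decrease to 90.4% in the group without SARS-CoV-2 antibodies". Allocation: "We have assumed a 2:1 ratio between those with and without SARS-CoV-2 antibodies". Error rates: "with 90% power and a 5% two-sided significance level". Required total: 9,273 per population.

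**Inputs not in the documents.** Other-cause mortality by antibody status is not given. The 6-month values below are assumptions, shown as a range.

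**Step 1: reproduce the plan's figure.** With event risks p1 = 0.076 and p2 = 0.096, the pooled risk is p = (2 × 0.076 + 0.096)/3 = 0.0827. The two-proportion formula for the negative group is

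n = [1.96 √(1.5 p(1 − p)) + 1.2816 √(p2(1 − p2) + p1(1 − p1)/2)]² / (p2 − p1)² = 3,072.

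The total is 3 × 3,072 = 9,216, which is 0.6% below 9,273. An exponential-survival formula gives 9,208. The stated figure reproduces.

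**Step 2: implied cause-specific ratio.** Taking 6 months as one unit of time and constant hazards, λ1 = −ln 0.924 = 0.07904 and λ2 = −ln 0.904 = 0.10093. The ratio is 0.10093/0.07904 = 1.277, and its log is 0.2444. This treats the planned percentages as infection rates in the absence of competing death, since the sample size text does not mention it.

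**Step 3: add competing death.** For assumed mortality m, the death hazard is δ = −ln(1 − m). Cumulative incidence at 6 months is F = λ/(λ + δ) × (1 − exp(−(λ + δ))). The subdistribution ratio is approximately ln(1 − F2)/ln(1 − F1).

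Example, 2% v 5%: δ1 = 0.02020 and δ2 = 0.05129, so F1 = 0.07525 and F2 = 0.09362. The ratio is 0.09830/0.07823 = 1.257, with log 0.2283. The share of the log ratio lost is 1 − 0.2283/0.2444 = 7%.

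**Step 4: check the approximation.** The large-sample Fine and Gray ratio was also solved from its expected score equation, with one third antibody-negative and no other censoring. Nominal power is Φ(3.24 k − 1.96), where k is the share of the log ratio kept.

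| Assumed mortality, positive v negative | F1 | F2 | Approximate ratio | Score-equation ratio | Log ratio lost | Nominal power |
|---|---|---|---|---|---|---|
| 1% v 1% | 0.0756 | 0.0955 | 1.2768 | 1.2768 | 0% | 90% |
| 1% v 2% | 0.0756 | 0.0951 | 1.2701 | 1.2702 | 2% | 89% |
| 2% v 4% | 0.0752 | 0.0941 | 1.2633 | 1.2635 | 4% | 87% |
| 2% v 5% | 0.0752 | 0.0936 | 1.2565 | 1.2568 | 7% | 86% |
| 2% v 8% | 0.0752 | 0.0922 | 1.2361 | 1.2367 | 13% | 80% |

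The cause-specific ratio stays at 1.277 in every row.

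**Step 5: an item 4 outcome.** With assumed COVID-19 death risks of 0.5% v 1%, the cause-specific ratio is ln 0.99/ln 0.995 = 2.005. The score equation gives 1.995 at 1% v 2% other-cause mortality and 1.985 at 2% v 4%, a loss of 0.7% and 1.5% of the log ratio. In this example the proportional loss is smaller than for infection.

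**The case against.** The strongest reply is that the model matches what the plan sets out to compare. Item 3 compares cumulative incidence, objective 3 speaks of risk, and the sample size targets the 6-month infection-free proportion. These are absolute-risk quantities. For them, a ratio of 1.257 where the cause-specific ratio is 1.277 is the correct answer and not a bias. This stands: Fine and Gray should stay, and what is missing is a companion estimate.

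A reader might go further and infer that the planned ratio will understate the association because antibody-negative patients are expected to have higher background mortality. The documents do not support that. Sections 1.1 and 4.2 tie poor antibody response to disease type, immunosuppression and rituximab, which makes a difference in mortality plausible, but no death rate by antibody status is given. The death in the Section 1.2 hypothesis reads as death from SARS-CoV-2. That normally follows infection, so it does not compete with it.

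Planned risk adjustment may narrow measured mortality differences, but it does not turn a subdistribution ratio into a cause-specific one. Nor does a cause-specific ratio isolate biology: the shielding behaviour described in Section 1.1 affects either model.

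The power argument is weak. Using D = N(2F1 + F2)/3 events and power Φ(ln(ratio) √(2D/9) − 1.96), the planned 10,200 results with no withdrawals give about 90% at 1% v 2% and 87% at 2% v 5%. Section 7 also expects Omicron to raise event rates, which would increase power further.

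Finally, Section 7 calls its list high-level and refers to an SAP. A secondary model might be specified there, but none appears in the text available, and the only detail expressly deferred is the choice of imputation variables.

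**Conclusion.** The point holds as a gap in the set of estimates, not as an error in the model chosen. The Fine and Gray ratio alone cannot separate the infection rate among the living from differential mortality, and the hypothesis and objective 3 need that separation.

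Direction and size are conditional. Attenuation is nil at equal mortality, 2% to 4% of the log ratio at 1% v 2% or 2% v 4%, and 7% to 13% at 2% v 5% or 2% v 8%. These figures rest on constant hazards, no covariate adjustment, the planning values of 92.4% and 90.4%, and mortality figures that are wholly assumed. If antibody-negative patients had the lower other-cause mortality, the ratio would move away from 1 instead. This is a minor, inexpensive improvement; the case for it is interpretation, not power.

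**What to change.** In Section 7, items 3 and 4, keep the cumulative incidence curves and the Fine and Gray comparison, labelled as addressing absolute 6-month risk. Beside them, prespecify for each outcome:

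- an adjusted cause-specific Cox hazard ratio by antibody status, with competing deaths censored and the same adjustment set as the Fine and Gray model;
- the cause-specific hazard ratio by antibody status for those competing deaths, with the competing event defined for each outcome (for infection, death before a proven infection; for COVID-19 death, death from any other cause).

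State in advance that the cause-specific ratio is used to interpret the antibody-infection association and the Fine and Gray ratio to describe absolute risk, so that the choice is not made after results are seen. Both registries should follow the same specification.

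No new data are needed, because handling death as a competing event already requires the dates of those deaths. The cost is one more standard model per outcome, the model for competing deaths, and two ratios per outcome to present and explain. If mortality proves similar in the two groups, the ratios will nearly agree, which is itself worth reporting.

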Serological responses to 2 vaccine doses are known to be influenced by clinical factors, such as disease type, type of immunosuppression, timing of immunosuppression in relation to vaccine and type of vaccine^{1,9}. The reported real-world clinical efficacy of SARS-CoV-2 vaccines in immunocompromised individuals in the UK is likely biased by patients' behaviour, with many continuing to self-impose shielding because of anxiety over lack of vaccine efficacy. Therefore, there is little data on true infection risk in this patient population, clinical factors contributing to lack of immunogenicity and clinical efficacy. Such information could help provide stratified advice to specific patient groups, rather than classify all immunosuppressed patients at risk. This information could also help estimate and/or identify the number of patients who may benefit from additional or alternative methods of prophylaxis, such as monoclonal antibody therapy^{10,11}.

The REal-time Assessment of Community Transmission-2 (REACT-2) study (IRAS ID 210407), used lateral flow immunoassays (LFAs) to track SARS-CoV-2 seroprevalence in the UK, coinciding with the vaccine roll out¹². Evaluating the prevalence of SARS-CoV-2 antibodies, coupled with sociodemographic information, provided informative epidemiological data. The LFAs used within the REACT-2 study

have been validated in a cohort of kidney transplant patients, with a test performance adequate to be used for population screening¹³. Using similar methodology to the REACT-2 study, we propose to investigate the proportion of immunosuppressed people with detectable SARS-CoV-2 antibodies following three and four vaccine doses, and correlate antibody status with subsequent infection risk and severity.

With the emergence of the Omicron variant, the UK government announced an expedited approach to the COVID-19 vaccination programme on 29th November 2021¹. This involved people who are severely immunosuppressed being eligible for a 4th vaccine dose 3 months after their 3rd primary dose. Early data from France, suggest that up to 42% of transplant patients will develop de novo antibody responses following a 4th dose, if they have previously been non-responsive^{2,3}. Antibody concentrations remain generally low in this population, however, and are unlikely to be associated with significant protection.

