As of 14th February 2022, 2,500 adult solid organ transplant recipients have self-registered with the trial web portal and returned the results of the LFIA they received following their 3rd vaccine dose. Depending on availability of LFIA kits, participants who had an initial negative test will be further invited to perform an additional LFIA test, after receipt of their fourth or subsequent vaccine dose. These additional tests will provide data on the proportion of transplant recipients who seroconvert after their fourth or subsequent vaccine dose, despite being negative for anti-SARS-CoV-2 IgG antibodies after their third dose.

People with cancer and autoimmune disease: A random selection of eligible patients with autoimmune disease or haematological malignancy registered on the NCARDRS and NCRAS databases respectively, will be invited to join the study via personalised letter. Up to 2 reminders will be sent to potential participants. Patients responding to the invitation will register via the Ipsos MORI web portal. Using the experience from REACT-2, we estimate a response rate of 70% at registration and 85% at lateral flow test completion.

Following registration on the web portal and completion of a short online questionnaire including information on immunosuppression and medical history, sociodemographic variables and COVID-19-related behaviours and COVID-19 infection history, participants will be sent a LFIA test, which is provided with a detailed instruction booklet and link to an instruction video. For consenting young persons aged 12-15, the LFIA kit will be addressed to the parent / guardian whose name they have provided. Participants will be asked to carry out the test and follow the instructions to read the result and to take a photograph of the completed test, if possible. They will then provide their results via the web portal. A telephone helpline will be established to deal with any queries that may arise. Usability of the test has been assessed in REACT-2 study.

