The lateral flow device to be used is the Fortress COVID-19 Total Antibody Device for the detection of IgM and IgG SARS-CoV-2 against the spike protein. The device has been evaluated for use in detecting anti-S in transplant patients and found to have a sensitivity of 92% and specificity of 95%¹³. The sample size calculation is described previously. The event rate of freedom from infection at 6 months in the group with antibodies was estimated from data in the PHE report "COVID-19 vaccine surveillance report - week 37". Table 2 of this report presents case rates per 100,000 for those who have received 2 doses of vaccine, which we have taken as our best estimate for event rates in a group with SARS-CoV-2 antibodies. The age-adjusted mean event rate from this data shows a 0.79% infection rate over a 4 week period in August 2021. Multiplying this up for our 6-month (180 day) follow-up period would suggest an event rate of 5.08%. However, this data relates to the UK population at large, not the higher risk immunosuppressed population that will be recruited to MELODY. Recent data on COVID-19 infection among those with rare autoimmune rheumatic disease showed that the age-standardised infection rate in this group was 1.54 times higher than in the general population¹⁷. We have therefore inflated our anticipated event rate by 50% to give the final event rate of 7.62% for this group (freedom from infection rate of 92.4%). Using the same process for the PHE data on unvaccinated individuals would suggest an infection rate 2.12% higher in the group with no SARS-CoV-2 antibodies. We have therefore powered the study to detect a 2% difference between those with and without antibodies. The statistical design and analysis was developed with co-applicants [name], [name] and [name].

1. JCVI advice on the UK vaccine response to the Omicron variant.
2. Kamar, N., et al. Assessment of 4 Doses of SARS-CoV-2 Messenger RNA-Based Vaccine in Recipients of a Solid Organ Transplant. *JAMA network open* **4**, e2136030 (2021).

3. Caillard, S., *et al.* Antibody response to a fourth mRNA Covid-19 vaccine boost in weak responder kidney transplant recipients. *medRxiv*, 2021.2009.2003.21262691 (2021).
4. Qin, C.X., *et al.* Antibody response to 2-dose SARS-CoV-2 mRNA vaccination in pediatric solid organ transplant recipients. *American Journal of Transplantation* **22**, 669-672 (2022).

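### The anti-spike LFIA cannot tell vaccine-induced antibody from an administered anti-spike monoclonal, and items 5 and 6 have no rule for recipients

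*Combined protocol and SAP*

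**What the plan says.** **The test.** Appendix 1 specifies "the Fortress COVID-19 Total Antibody Device for the detection of IgM and IgG SARS-CoV-2 against the spike protein".

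**How a positive is read.** In Section 7, item 5: "Logistic regression models will be used to identify which of these factors are independently associated with developing antibodies", with completion of the primary vaccine course as the reference point. Item 6 reports the proportion of re-sampled transplant recipients "with and without antibodies to SARS-CoV-2 following 4th dose who did not have antibodies after 3rd dose". Section 4.3 says that the re-tests give "data on the proportion of transplant recipients who seroconvert after their fourth or subsequent vaccine dose".

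**What is collected.** Section 4.3 describes a "short online questionnaire including information on immunosuppression and medical history, sociodemographic variables and COVID-19-related behaviours and COVID-19 infection history". The linked data named in Sections 4.2 and 7 are vaccination, RT-qPCR infection, hospitalisation and death. Eligibility in Section 4.2 rests on registry group, age and three vaccine doses. Section 7 adjusts for other known risk factors and a later 4th dose.

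**Administered antibody.** Section 1.1 says that the results could help identify patients who may benefit from "additional or alternative methods of prophylaxis, such as monoclonal antibody therapy", and cites two studies of a monoclonal combination, one in treatment and one in prevention. Administered antibody is not taken up in the eligibility, data collection or analysis sections.

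**The concern.** The device reports whether anti-spike antibody is present, not where it came from. Items 1 to 4 need only presence. Items 5 and 6 go further and attribute a positive to vaccination. A participant who made no antibody but had been given an anti-spike monoclonal would usually test positive and be entered as having developed antibodies.

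In item 5 this moves non-responders into the responder category. If receipt is more common in some clinical groups than in others, it distorts the odds ratios meant to identify who fails to respond. In item 6, a product given between the two tests would appear as response to dose 4. Participants re-tested there have already tested negative once, and the background section has such patients in view for alternative prophylaxis.

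Covariate adjustment does not repair an outcome that has been recorded wrongly. Nor does the quoted specificity cover the problem. Its reference standard is itself serological, so administered antibody could be positive on both the device and the reference.

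**Working it through.** **1. The plan's own precision.** Inputs from Section 7: 10,200 results per population, one third without antibodies.

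1.96 × √[(1/3)(2/3)/10,200] = 0.91 points; at 50%, 0.97 points. Both stated half-widths reproduce.

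**2. Inputs for the size of the effect.**
- True non-responders: 1/3 of 10,200 = 3,400 (Section 7).
- Sensitivity 92.0%, specificity 95.1% (Section 7, diagnostic accuracy).
- *s*, the share of true non-responders carrying administered anti-spike antibody at the test: not in the documents; assumed 1% to 10%, with 20% added for item 5.
- Administered antibody is assumed to be detected as often as a participant's own (92%).

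**3. Proportion testing negative.** A true non-responder tests negative with probability 0.951. With administered antibody this becomes 1 − 0.92 = 0.08. The difference is 0.871, so shift = (1/3) × *s* × 0.871.

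| *s* | Non-responders affected (of 3,400) | Shift (points) |
|---|---|---|
| 1% | 34 | 0.29 |
| 3% | 102 | 0.87 |
| 5% | 170 | 1.45 |
| 10% | 340 | 2.90 |

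The shift reaches 0.91 points at *s* = 0.0091 × 3 / 0.871 = 3.1%. It is bias, so sample size does not reduce it.

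**4. Item 5, illustration.** Assume true non-response of 60% in one group and 20% in another (odds ratio 6.0), with administered antibody only in the first.

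Assay error alone: 0.60 × 0.951 + 0.40 × 0.08 = 0.603 test negative in the first group, and 0.20 × 0.951 + 0.80 × 0.08 = 0.254 in the second. The odds ratio is 4.45. This is the fair baseline, because ordinary misclassification is there anyway.

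Adding administered antibody: 0.603 − 0.60 × *s* × 0.871.
- *s* = 5%: 0.576, odds ratio 3.99
- *s* = 10%: 0.550, odds ratio 3.59
- *s* = 20%: 0.498, odds ratio 2.91

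**5. Item 6.** Take the cited upper figure of 42% de novo response after dose 4 (Section 1.1) as the true rate, so 58% remain non-responders. If a share *s* of those received a product between tests, apparent seroconversion rises by 0.58 × *s* × 0.871, which is 1.5, 2.5 or 5.1 points at 3%, 5% or 10%. This ignores false negatives at the first test.

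**6. Is excluding recipients enough?** Suppose every recipient is a true non-responder. Exclusion then removes only non-responders, and the true proportion among those left is (1/3)(1 − *s*)/(1 − *s*/3): 32.2% at 5% and 31.0% at 10%, against 33.3%. On the tested scale the remaining bias is (33.33 − 32.20) × 0.871 = 0.98 and (33.33 − 31.03) × 0.871 = 2.00 points. Set against 1.45 and 2.90 with no action, about two thirds remains.

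For the illustration in step 4, non-response in the first group after exclusion is 0.60(1 − *s*)/(1 − 0.60*s*). Multiplying by 0.871 and adding 0.08 gives the proportion testing negative, and odds ratios of 4.25, 4.06 and 3.66 at 5%, 10% and 20%. Against the baseline of 4.45, roughly half the attenuation remains.

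**The case against.** **The questionnaire may already ask.** Its topics are introduced as examples, they include immunosuppression and medical history, and the form itself is not in the documents. This stands. A reader might infer that receipt is not asked about; the text supports only that it is not named. Even if it is captured, no analysis rule in Section 7 uses it.

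**Section 7 is a high-level plan.** It leaves room for adjustment for other known risk factors. That does not help here, because the error is in the outcome.

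**Most outcomes are indifferent to origin.** The objectives in Section 2 speak of detectable antibodies and antibody status, and items 1 to 4 of people with and without antibodies. A recipient does have detectable antibody. A reader might infer that items 1 to 4 are wrongly defined; they are not. The difficulty rests on the wording of items 5 and 6 and of the re-test paragraph.

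**Other products and who receives them.** A reader might extend the point to pooled immunoglobulin, or assume that antibody products go mainly to the weakest responders. The documents mention neither. The monoclonal point is itself an inference from the device's spike target, and Section 1.1 speaks of monoclonals as something patients may benefit from, not as something participants have had.

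**The size is hypothetical.** Every frequency above is assumed. In the illustration, ordinary assay error (6.0 to 4.45) moves the odds ratio more than a 10% share of administered antibody does (4.45 to 3.59). This stands, and it limits how strongly the point can be put.

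**Conclusion.** The concern holds for items 5 and 6. The plan attributes a positive anti-spike result to vaccination and names no means of separating participants given anti-spike antibody, although its own background makes that exposure foreseeable. Any recipient who did not respond to vaccine would usually be counted as a responder.

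The size cannot be established from the documents. At about 3% of true non-responders affected, the shift matches the stated half-width of 0.91 points; at 5% and 10% it is 1.5 and 2.9 points. These figures assume that one third are true non-responders, that the stated sensitivity and specificity apply, and that administered antibody is detected as often as a participant's own. The odds-ratio figures also rest on an invented 60% versus 20% contrast with receipt in one group only.

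The documents do not show that any participant has received such a product, or that the study's stated precision or sample size is wrong. This is an inexpensive improvement that should be made. Confidence is moderate because the frequency is unknown and the questionnaire is not shown.

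**What to change.** **Data.** If not already captured, add one dated question at registration and at re-test: receipt of any SARS-CoV-2 antibody product. Other antibody-containing products can be recorded in the same item.

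**Items 5 and 6.** Report results (a) excluding participants with receipt before the relevant LFIA, within a window fixed in the SAP, and (b) counting those recipients as non-responders. Version (b) is an upper limit for the proportion not responding. Version (a) is a lower limit provided recipients responded no better than comparable non-recipients, so under that condition the two bound the proportion. For an odds ratio the bounding is clean only when receipt is concentrated in one of the groups compared, so show counts of recipients by group.

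**Items 1 to 4.** Keep the primary definitions and show results with and without recipients as a sensitivity analysis.

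**Cost.** One question and a short SAP rule. Version (a) loses some participants: removing 5% or 10% of 10,200 widens the half-width at one third from ±0.91 to ±0.94 or ±0.96 points. Receipt would be self-reported. Information will be incomplete for transplant participants already tested (2,500 had returned results by 14 February 2022). Re-test invitations go only to those initially negative and depend on kit supply, and Section 6 ends direct involvement once the result is uploaded. Those already positive after dose 3 would be missed unless a new contact were added. State this as a limitation.
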